To this end, a group of psychologists, social science researchers, and interactive-web designers have begun to create an online program to deliver to Veterans an ACT for Chronic Pain online intervention (VACT-CP). However, often when such online interventions for Veterans are created, major stakeholders – clinicians, nurses, and other care providers – are not included in the iterative development and feedback process, although best practices suggest this is vital (Schueller et al., 2014). As these are often the primary source for potential Veteran referrals to such online programs, this is a major gap in much of the literature on developing, assessing, and refining such systems for use by Veterans. To address this gap and create a usable online intervention, and systematically include these providers in the ongoing VACT-CP development process, we will first conduct qualitative interviews with 10 - 12 current chronic pain providers (including social workers, physicians, PACT nurses, and psychologists) who provide treatment for chronic pain at the VA Bedford Healthcare System for formative assessment of the potential benefits, concerns, and institutional VHA dissemination issues for the VACT-CP intervention.

In addition, we will interview and gather feedback from Veterans (12 – 15) to for usability testing, to assess the delivery mode, and utilize an Integrated Technology Acceptance Model to iteratively assess feasibility and usability of the VACT-CP online treatment. This portion of the project will focus on refining the delivery mode, and revising chronic pain intervention content as necessary. Specifically, providers and Veterans will be shown the VACT-CP system for intervention and interviewed about their reactions in order to allow for system refinement and to allow for revisions to the system. **This project will thus aim to:**

Phase 1 Objective: To gather qualitative feedback on the VACT CP system from a sample of 10 - 12 chronic pain clinical-care providers, as well as explore and identify barriers and facilitators of VACT-CP referrals and implementation in the VA Bedford Healthcare System.

1. VA Bedford providers will be interviewed individually to aid in ongoing VACT-CP development, and to gather information on potential opportunities and barriers to referring Veterans to the online VACT-CP program.

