 - 1a. Open-ended questions related to palatability of the intervention, feasibility of engagement with Veterans with chronic pain, interest or potential concerns with referring Veterans to such a program, and reactions to a short walk-through of the intervention.
 - 1b. Gather more general information from valuable stakeholders and potential referral-providers to discover possible benefits, barriers, referral concerns, and overall thoughts on online Veteran interventions.
2. Providers will be interviewed in the context of planning for a future pilot usability trial of VACT-CP (IRB application for this trial will be submitted separately in the future), to adapt the program and recruitment strategy to the Veteran needs and local context.

Secondary Aims: N/A

Phase 2 Objective: Conduct a Feasibility and Usability Assessment to pilot test VACT-CP components including format, ECA, and system usability via field-based iterative usability testing (3 rounds, n = 4-5 per round, total n = 12 – 15).

1. Gain further feedback on the VACT-CP treatment by gathering information from Veterans via usability testing (n = 12 – 15 total).
2. Assess Veteran interest, satisfaction, and usability of the online VACT-CP program.
3. Iteratively address any technological concerns.
 - a. Utilize Veteran feedback, website revisions, and preliminary support that a small-pilot RCT is merited.

Phase 3 Objective: The goals of the feasibility pilot RCT study phase are to conduct a Stage 1b RCT pilot trial (total recruited n = 40 – 60 participants) to:

1. Explore relationships between Veteran traits, usability beliefs, and technology perceptions on intended and actual use of the VACT-CP system
2. Describe differences in VACT-CP versus a wait-list control group on pre- and post-test measures of pain acceptance, pain level, pain-related functioning, and quality of life, treatment satisfaction with the VACT-CP system and ACT-related outcomes including pain acceptance, valued living and experiential avoidance;

3. Evaluative the relative feasibility and acceptability of the VACT-CP intervention procedure and waitlist control, including ease of recruitment, retention in each condition, treatment receptivity, attrition and retention in each condition, sustained participation, and the assessment process.

A maximum of 40 Veterans will be enrolled and randomized to test the VACT-CP system within their home; we will recruit up to 60 participants in order to meet this randomization goal.

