3.2 Type of Study

Phase One: We will first finalize the design of a mock-up of the VACT-CP website, and some finalized portions of the VACT-CP treatment that will be shown during usability interviews to elicit feedback and further refine the online program and website. For Phase 1, we will conduct semi-structured interviews with a maximum of 12 providers at the VA Bedford Healthcare System, who report working at least partially on issues of chronic pain. These interviews will be audio-recorded for formative assessment of the potential benefits, concerns, and institutional VHA dissemination issues for the VACT-CP intervention, using a semi-structured interview guide and a “think-aloud” strategy for intervention review. Providers will also be shown the VACT-CP system for intervention and interviewed about their reactions to the site, and queried regarding the potential benefits, barriers, referral concerns, and overall thoughts on the VACT-CP system. These interviews will be audio recorded. We will also ask participants to complete a very brief (5 minute) questionnaire related to their work background and general demographics in order to describe our provider sample. The generated information and themes will be utilized for development and refinement of the VACT-CP intervention and to learn from major stakeholders the important areas for potential revision during development and inform development of the full-VACT-CP system.

Phase Two: We will conduct semi-structured interviews with a maximum of 15 Veterans with chronic pain. The goals of Phase 2 are to: 1) gain further feedback on the VACT-CP treatment by gathering information from Veterans via usability testing to; 2) assess Veteran interest, satisfaction, and usability of the online VACT-CP treatment; 3) iteratively address any technological concerns. For purposes of feedback and iterative program development, the Veteran will be provided with portions of the VACT-CP intervention, which they will access on a personal computer, during which time their use of the system will be recorded using either VA Skype for Business or Cisco WebEx. Approximately 4 - 5 Veterans will be recruited and participate in this usability testing at a time, with 3 different usability testing arms, in order to allow for time to iteratively address any functionality issues or concerns with

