3.3 Study Procedures

a. Sub-Study Participation

N/A

b. Study Related Procedures

General Procedures

Phase One: All Primary Aims will be assessed through a qualitative interview with a research staff member at the VA Bedford Healthcare System. Subjects will be VA clinical care providers. Upon obtaining IRB approval, research project staff will provide study information to VA staff and clinicians within clinics serving Veterans with chronic pain such as social work, Primary Care and Behavioral Health, etc. Providers may also call the listed research staff contact number on the informational materials if interested in study participation after seeing a flyer or hearing about the study. Sampling for this group will also be based on a reputation-based snowball design. Research staff will then coordinate with the provider to answer any questions about the study and provide a time to complete informed consent and the qualitative interview, which should take approximately 1 -1.5 hours total. Confidential and private spaces at the VA Bedford Healthcare System will be used for the qualitative interview, and the website prototype will be shown on one of the computers within this room. A total of 10 – 12 providers who identify as treating patients with chronic pain will be enrolled.

Phase Two: Usability testing procedures: We will conduct usability testing with 12 - 15 Veterans who meet eligibility criteria. We will first complete a phone screen, to assess whether Veterans are eligible according to our inclusion/exclusion criteria. After the intake assessment, eligible participants will be scheduled for usability testing (a one session procedure). The intake assessment may be completed remotely VA Skype for Business or Cisco WebEx, depending on their system eligibility, as both are approved for current use in VA research.

Usability testing will be conducted in three waves, with 4-5 participants in each wave. The choice of 4 - 5 participants per wave was based on the finding that approximately 80% of usability problems can be

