During each wave of testing, Veterans will interact with the VACT-CP online treatment to: 1) gather feedback regarding acceptability and usefulness of the treatment, 2) gather and analyze complementary data from SUS-8, 3) address any technological issues as they arise, and 4) examine preliminary data from this phase of the study. Modifications to the website will be based upon: 1) acceptability and feasibility of the online treatment, and 2) qualitative feedback obtained from patients, therapist, and mentors. Individual feedback sessions at the end of Phase 2 will be held to gather information for refining the treatment intervention and make it acceptable to patients.

We anticipate that our Veteran intervention reviewers might miss bugs or other user interface problems and anticipate that some revisions to the online system and program may need to be made. For instance, one potential issue that may arise might be an inability for the Veteran to read the text on the screen. After receiving this information during an initial feedback round, the researchers will amend the program with a potential solution, i.e., text size or text color being altered, with the revised version then being piloted in the next round of Veteran user testing. Some usability challenges will be addressed with introductory handouts/tutorial materials/orientation to the program at the beginning of the intervention session. In addition, large organizational issues will be discussed before moving on to platform refinement.

Phase 3: Data Collection

Callers will be initially screened by phone. Eligible participants will be scheduled for an in-person assessment or phone-conference with research staff. At this assessment, research staff will confirm study eligibility and obtain informed consent and administer the Structured Clinical Interview for DSM-5

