4.5.2 Enrollment

Phase One: 10-12 subjects will be enrolled in the study by study research staff. A subject will be considered enrolled in the study after the informed consent process.

Confidential and private spaces at the Bedford VA will be used for informed consent process, and for the single in person study visit. Interviews and questionnaires done in person in the VA will be completed with the door closed. A white-noise machine will be used whenever possible to further decrease the risk of participant information being overheard outside of the assessment room.

Phase Two: A maximum of 15 subjects will be consented in the study for usability testing. We assume that for every 3 people we consent, 2 will meet eligibility criteria and participate. For participants eligible for the usability testing session, a subject will be enrolled in the study after the informed consent process if they meet eligibility criteria.

Phase Three: A maximum of 60 subjects will be consented in the study. We assume that for every 3 people we consent, 2 will meet eligibility criteria and become enrolled in the study. For participants eligible for the usability testing session, a subject will be enrolled in the study after the informed consent process if they meet eligibility criteria.

4.5.2a HIPAA Authorization

Phase One: Not applicable. We are not asking providers about their health or healthcare, therefore HIPAA does not apply to this study.

Phase Two: We are requesting a HIPAA waiver from the IRB, as it may be impracticable to obtain a signed HIPAA document from subjects as all research activities will occur remotely. If they do not send back a written HIPAA document we would not be able to use their data.

Phase Three: We are requesting a HIPAA waiver from the IRB, as it may be impracticable to obtain a signed HIPAA document from subjects as all research activities will occur remotely. If they do not send back a written HIPAA document we would not be able to use their data.

4.5.2b Informed Consent:

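### Phase 2: a cap of 15 consents and an assumed 2-in-3 yield after consent give an expected 10 Veterans tested, so they cannot stand alongside the planned 12 to 15

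*Combined protocol and SAP*

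**What the plan says.** Three statements about Phase 2 size matter here.

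- **Cap.** Section 4.5.2 (Phase Two): "A maximum of 15 subjects will be consented in the study for usability testing". Section 3.2 sets the same ceiling on interviews: "We will conduct semi-structured interviews with a maximum of 15 Veterans with chronic pain". Section 4.1 also limits Phase 2 recruitment to 15.
- **Yield.** The sentence after the cap in section 4.5.2: "We assume that for every 3 people we consent, 2 will meet eligibility criteria and participate". The third sentence of that paragraph makes enrolment follow the consent process, on condition that eligibility is met.
- **Target.** Section 1.0 says "we will interview and gather feedback from Veterans (12 – 15") and gives the layout as "iterative usability testing (3 rounds, n = 4-5 per round"). Section 3.3 is explicit that this count is taken after any loss for ineligibility: "We will conduct usability testing with 12 - 15 Veterans who meet eligibility criteria".

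The Phase Three paragraph of section 4.5.2 repeats the 2-in-3 assumption, with a cap of 60 consents. Sections 1.0 and 3.3 give 40 randomized as the Phase 3 target.

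**The concern.** The cap and the yield are adjacent sentences, and their product falls below the lower end of the target. A consent maximum is an operating limit. Staff who had consented 15 and tested 10 would have no stated authority to consent replacements, and no section provides for any.

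The waves run in sequence, so a shortfall would fall mainly on the last one. Section 3.4 relies on successive waves to check each change, "with the revised version then being piloted in the next round of Veteran user testing". Changes made after the second wave can be checked with Veterans only if the third wave is adequately filled.

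**Working it through.** **Inputs, all from the protocol**

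- Phase 2 consent cap: 15 (section 4.5.2)
- Share of consented Veterans who prove eligible and participate: 2/3 (section 4.5.2)
- Planned number tested: 12 to 15, in three waves of 4 to 5 (sections 1.0 and 3.3)
- Phase 3 consent cap 60, same share 2/3, target 40 (sections 4.5.2, 1.0 and 3.3)

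**Step 1. Check the rule on Phase 3.** Expected number = cap x yield = 60 x 2/3 = 40. This reproduces the stated target exactly, so the rule is being read as the protocol uses it: the cap is set above the target to absorb the loss.

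**Step 2. Apply it to Phase 2.** 15 x 2/3 = 10, and 10/3 = 3.3 per wave. The smallest planned total is 3 x 4 = 12. The Phase 2 cap equals the top of the target range and has no allowance for loss.

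**Step 3. Chance of reaching the target by luck.** Let X be the number tested, and assume that each consented Veteran independently has a 2/3 chance, so X ~ Binomial(15, 2/3).

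- P(X ≥ 12) = 0.130 + 0.060 + 0.017 + 0.002 = 0.209
- P(X = 15) = (2/3)^15 = 0.002

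**Step 4. Effect on the third wave, if the rate is real.** Filling the first two waves takes 8 to 10 Veterans, or 8/(2/3) = 12 to 10/(2/3) = 15 expected consents. That leaves 3 to 0 consents, an expected 2 to 0 Veterans.

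**Step 5. What would make the figures agree.**

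With the cap kept at 15, the yield after consent would have to be 12/15 = 80% for an expected 12, and 15/15 = 100% for 15. At 80%, P(X ≥ 12) = 0.648.

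With the yield kept at 2/3, the consents needed are 12/(2/3) = 18 for an expected 12, and 15/(2/3) = 22.5, rounded up to 23, for 15:

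| Consents | Expected eligible (no stop) | P(at least 12) | P(more than 15) |
|---|---|---|---|
| 15 | 10.0 | 0.209 | 0 |
| 18 | 12.0 | 0.609 | 0.033 |
| 20 | 13.3 | 0.809 | 0.152 |
| 23 | 15.3 | 0.952 | 0.481 |

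The last column shows why a higher cap needs a stopping sentence: section 3.2 allows at most 15 interviews. With a cap of 23 and consenting stopped at 15 tested, the expected number of consents is 21.4, and the expected number tested is 21.4 x 2/3 = 14.3.

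**The case against.** The strongest reply is that the one-third loss will not happen after consent. Sections 4.1, 4.5.1 and 4.5.1b put a phone eligibility screen before the session, and 4.5.1b takes consent at the start of the session. Veterans who reach consent should then nearly all be eligible, and 15 consents could yield 12 to 15 tested. This is a fair reading, but it makes the 2-in-3 sentence wrong rather than removing the conflict. Nor do the documents settle it. Section 4.5.2 lets eligibility be judged after consent. Section 3.3 says "After the intake assessment, eligible participants will be scheduled for usability testing (a one session procedure"), while sections 4.5.1b and 4.5.2b put consent before any data collection or study procedure. Some loss after consent is therefore possible.

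It can also be said that Phase 2 is qualitative and descriptive, that several sections give the wave sizes or totals only as approximate, and that 10 is just 2 below the lower bound. Section 4.1 reports 2,605 Veterans seen for chronic non-cancer pain in a year, so supply is not limiting. All of this stands and keeps the point modest. It does not make 10 fill three waves of 4.

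A reader might infer three stronger things that the documents do not support:

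- **That Phase 2 will test only 10 Veterans, with a nearly empty third wave.** This follows only if the 2-in-3 rate is real, which is the open question.
- **That the 2-in-3 rate belongs to the phone screen.** No section gives a Phase 2 screening pass rate, so moving the figure there would be a guess.
- **That smaller waves would find materially fewer usability problems than section 3.3 expects.** That section cites about 80% for a sample of 4 to 5 and gives no rate per user. Any modelled loss at 3.3 users is no larger than the difference between 4 and 5 users that the plan already accepts.

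**Conclusion.** The inconsistency is real and needs no outside figure. In the Phase Two paragraph of section 4.5.2, the cap of 15 consents and the 2-in-3 yield give an expected 10, against 12 to 15 planned. The 21% chance of reaching 12 rests on one added assumption, that Veterans are independent with the same 2/3 chance. The expected value of 10 does not need independence.

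The documents do not show which of the three statements is wrong, so this is not a forecast that Phase 2 will fall short. No hypothesis test is affected. What is at stake is whether the stated number tested, and a full third wave, can be delivered under the written cap. The point is worth correcting because the remedy is small.

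**What to change.** The sponsor should confirm where Phase 2 eligibility is settled, then correct section 4.5.2 in one of two ways.

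**(a) If it is settled by phone before consent.** Keep the cap of 15. Delete the 2-in-3 sentence, or replace it with a participation rate after consent that is consistent with 12 to 15; at least 80% is needed for an expected 12. Do not reassign 2-in-3 to phone screening unless the sponsor has a basis for it. Cost: one sentence.

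**(b) If a one-third loss after consent is real.** Choose one of these:

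- Restate the expected number tested as about 10, and change the totals and wave sizes wherever they appear. Cost: text edits only, but the plan accepts a smaller phase.
- Set the consent cap between 18 (expected 12) and 23 (expected 15 before any stop), and state that consenting stops once 15 have been tested. Align the recruitment wording in sections 3.2, 3.4, 4.1 and 4.5, which would otherwise conflict with the higher cap. Cost: those edits and 3 to 8 more permitted consents. At a cap of 23 with the stop, the average is 21.4 - 15 = 6.4 more. The maximum of 15 tested is unchanged.

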4.6 Risk/Benefit Ratio

4.6.1 Potential Risks and Methods to be Used to Minimize Risks:

4.6 Risk/Benefit Ratio

4.6.1 Potential Risks and Methods to be Used to Minimize Risks:

Potential Risks:

This study does not require invasive procedures or investigational drugs. The major safety concern associated with this study is the disclosure of confidential information and is discussed in the confidentiality section below.

During the study assessments and study procedures, participants may experience some discomfort from discussing personal material and completing self-report questionnaires. Likewise, some participants may feel uncomfortable about having the study assessments and/or usability testing sessions videotaped and reviewed by others (which is necessary for usability testing analysis). Secondly, there is a possibility that study patients will not improve from the online intervention. In addition, The Columbia Suicide Severity Rating Scale will be used to assess and address any potential risk associated with participating in the study at each assessment session (i.e., baseline, post-treatment, etc.). Using results from this measure, study staff will be trained to immediately evaluate responses the Columbia and respond accordingly to the standard operating practice we have implemented in the protocol should the participant requires immediate crisis intervention.

There is a risk of breach of confidentiality and loss of privacy, which great care will be taken to prevent. As discussed below, we will take precautions to ensure that potential risks are minimized.

Adequacy of Protection Against Risk

Phase One: Potential risks are characterized as not greater than minimal. This study will pose no physical risk to subjects or investigators. The primary risk to individual subjects is that of a breach of confidentiality or that supervisors may view participation in this study as unfavorable. Appropriate steps will be taken to protect subjects' privacy and confidentiality. Interviews will take place in a confidential setting, behind a closed door, with just the participant and a research staff member at VA Bedford. Participation in the study is not anticipated to be associated with any substantial discomfort or

inconvenience. Minor inconveniences include time requirements, which may be viewed as frustrating and time-consuming. Providers may benefit from the knowledge that they helped to modify and test an implementation strategy that can be used as a tool for expanding treatment options for Veterans. These benefits outweigh the small risk of loss of privacy and confidentiality.

We will specifically guard against loss of confidentiality and supervisor influence in reference to interviews. Interviews will take place in a private room and will not involve clinic leadership or a participant's supervisor. No personally identifiable information (PII) will be collected.

All identifying information will be maintained in locked file cabinets in locked offices or on a VA-secured server. The electronic contact list will be password protected and stored on a VA shared drive and will only include names and phone numbers of interested providers. All information will be kept according to VA Records Retention Policy. This information will be only be used for scientific research purposes. Only VA study team members will have access to this information. The study team will not identify, directly or indirectly, any individual participant in any report of such research or otherwise disclose participant identities in any manner. Providers who decide they want to participate will need to sign an Informed Consent prior to entering the study. This consent form will provide detailed information about study procedures and potential risks and benefits.

Participants will be asked not to identify themselves or other staff by name in interviews and transcripts will have any names of individuals removed. Interviews will be digitally recorded and kept on VA servers behind the VA firewall and in accordance with VA policies. Each digital recording will be identified by a unique code that will NOT include subject identifiers. Transcription of digitally recorded material will take place on VA servers behind the VA firewall by a VA research assistant or using a VA-approved transcription service. Transcripts will be identified by a unique code that will NOT include subject identifiers. Only research staff members approved by the human subjects committee will have access to participants' research records. All research information will be kept behind VA firewalls or will be securely stored in locked file cabinets in locked offices.

Phase Two and Phase Three: Recruitment procedures have been described under Research Design and Methods above. Participants will be obtained from referrals from Bedford VA services and clinics, including primary care, the mental health clinic, and specialty services (e.g., MHICM, domiciliary, Women's Health Clinic, OEF/OIF program, Vietnam Veteran groups, LGBTQ program). We expect that some participants will be self-referred, whereas others will be referred by providers.

Verbal informed consent will be obtained from each participant prior to entering the study. The informed consent document will explain in simple terms, before the Veteran is entered into the study, the risks and benefits to the Veteran. The informed consent document will contain a statement that the consent is freely given, that the Veteran is aware of the risks and benefits of entering the study, and that the Veteran is free to withdraw from the study at any time. Consent will be obtained after a thorough explanation of the study by the PI or study staff member and an opportunity for the participant to ask questions about the study. This discussion will take place under conditions in which the participant has adequate time to consider the benefits and risks associated with his/her participation in the study. The IRB-approved consent form will be signed and dated by the participant and investigator and a witness. A discussion of the study's purpose, research procedures, risks and potential benefits, and the voluntary nature of participation as part of the informed consent process will continue throughout the research experience.

It will be the responsibility of the PI to assure that an informed consent form is obtained from each participant or legal representative and to obtain the appropriate signatures and dates on the informed consent document prior to the performance of any protocol procedures and in accordance with current state and federal regulations. Documentation of informed consent document will be retained within study records.

Data Storage and Privacy

All information about subjects will be protected by the research team who will follow all guidance provided in the following VHA HANDBOOKS and DIRECTIVE:

- VHA HANDBOOK 1605.1, PRIVACY AND RELEASE OF INFORMATION (May 17, 2006)
- VHA HANDBOOK 1907.01, HEALTH INFORMATION MANAGEMENT AND HEALTH RECORDS (August 25, 2006)
- VHA HANDBOOK 6500, INFORMATION SECURITY PROGRAM (September 18, 2007)
- MEMORANDUM, SUBJECT: Protecting Information Security and Privacy (February 27, 2009)
- VHA HANDBOOK 1200.12, USE OF DATA AND DATA REPOSITORIES IN VHA RESEARCH (March 9, 2009)

All data collected will be the property of the Department of Veterans Affairs whether in paper or electronic form and will be secured utilizing the following methods.

Paper:

- All paper documents will be stored on VA property unless authorized by the Director, Information Security Officer, and Privacy Officer in writing.
- All paper documents will be locked in an approved file cabinet with only members of the research team having access.
- Paper documents will be stored at the Bedford VA in Building 5.

Electronic:

- All information in electronic form will be stored on VA servers at the VA Bedford Healthcare System behind the VA firewall.
- Electronic Data Associated with this study will be located on secure VA servers.

The people or agencies that will have access to the information are the principal investigator and the co-investigators. No information related to this research will be released to any third party or disclosed outside of the VHA – except as required or permitted by law. Subjects' identity will not be revealed in any reports or publications resulting from this study.

Risk of injury: We do not anticipate any injuries associated with this study. However, as mentioned in the informed consent, no money has been set aside for compensation in case of injury as a result of participating in this study however subjects have the right to file any legal action.

Adequacy of Protection Against Risks:

Phase One: To ensure protection of confidential information, all data will be coded and stored in locked files to ensure confidentiality. Each digital recording will be identified by a unique code that will not include subject identifiers. Transcription of digitally recorded material will take place on VA servers

behind the VA firewall and by a VA-approved research assistant. Transcripts will be identified by a unique code that will not include subject identifiers. Completed quantitative information will be kept at the data management site at VA Bedford Healthcare System and stored in password protected files on a VA secure server folder, designated for this study only. Only the PI and the PI's research team will have access to the computerized data. Research staff working on this study will be educated about the importance of strictly protecting subjects' rights to confidentiality.

In addition, The VA Bedford Healthcare System has an institutional policy requiring all clinical investigators and their key personnel to undergo mandatory training in human research subject's participation. The program includes all clinical researchers regardless of their source of funding. Researchers typically fulfill this requirement by completing VA mandated research trainings. [name] and other staff have successfully completed this education in human subjects research.

Phase Two: To protect Veterans against risk the following steps will be taken:

- 1) In order to minimize anxiety during the study assessments and usability testing, the PI and study staff will make every attempt to help participants feel comfortable when discussing sensitive material or talking aloud during the usability testing procedure. The PI is a licensed clinical psychologist with 10 years of clinical experience, particularly with regard to treating anxiety, depression, PTSD, mood-related issues due to serious health conditions.
- 2) Initial and continuing participation of the participant in these protocols will be strictly voluntary; the participant will remain free to terminate participation at any time.
- 3) Data will be collected directly from the participants. All data will be used specifically for the research purposes described in this application. No identifying information will be associated with any information provided by participants as a function of their participation in this study, including their names, addresses, or phone numbers. Each participant in the study will be assigned an arbitrary study number at random and this number will be used for all data for subsequent analyses. Although the screening log will include the name of each participant, it will be filed separately from the actual data files for each participant. To ensure protection of confidential information, all data will be coded and stored in locked files to ensure confidentiality. Video and audio data within the recordings of usability testing will be kept at the data management site at the Bedford VA and stored on a secure VA server for this study. Upon completion of the study and data entry and analysis data will be stored according to VA regulations and destroyed 6 fiscal years after the close of the study. Only the PI and the PI's research team will have access to the computerized data. Names will not be included on videotaped portions of the study, in computerized data files, or in any published reports. Case records will be reviewed only by study personnel or, if necessary, by institutional, state, or federal regulatory personnel. Research assistants and others working on this study will be educated about the importance of strictly protecting participants' rights to confidentiality.
- 5) Numerous safeguards will keep electronic data secure. Each subject will be assigned a code number so that should any non-study personnel gain access to the data, they will not know to whom the data belong. A secure password is required to access computers at each site, and computer networks are on secured servers that meet or exceed federal confidentiality standards. All connections to this website will be made using the secure sockets layer (SSL). Participant usage data are maintained on a server in a locked server room at Northeastern University, where the VACT-CP website is hosted. Full access to

the server is restricted to two staff members. VACT-CP will store participant usage data. **No participant identifiers will be transmitted to this database server. The VACT-CP website will only store data related to site usage during usability testing.**

6) The Bedford VA has institutional policies requiring all clinical investigators and their key personnel to undergo mandatory training in human research participant's participation. The program includes all clinical researchers regardless of their source of funding. Researchers typically fulfill this requirement by completing Bedford VA research trainings. All research staff have successfully completed education in human subjects research through the Bedford VA.

Phase Three: To protect Veterans against risk, the same steps as Phase 2 will be followed. In addition, we will take the following steps during the research process:

- 1) Potential study participants will be screened initially over the phone for eligibility. For screening purposes only, this study will maintain a contact log. This log will contain the identifying information for veterans who are identified by research staff via medical record review or who contact research staff after learning about the study. It will contain the veteran's name, social security number, contact information, and status (No Response, Screened In, Screened Out, Pending, Chose not to participate). This log will be password protected and stored on a VA shared drive. This log will be maintained until the end of the recruitment period in order to prevent ineligible or uninterested veterans from being contacted again by letters from providers or by research staff. The identifiable information will be used only by members of the research team. This information will not be disclosed to anyone outside the VA. The proposed study poses minimal risk to the privacy of the subjects because all data will be stored on secure servers, the intervention website (VACT-CP) will not collect any PII or PHI, and all assessments will take place using a secure space at the VA, our VA-approved Qualtrics system for surveying participants, or using a VA-approved secure teleconferencing system (MS Teams, Cisco, WebEx, phone calls, etc). Study screening forms will be coded, and will not contain the veteran's name, social security number, or date of birth. All identifying information will be maintained in locked file cabinets in locked offices or on a VA Shared Drive.
- 2) There is a possibility that study participants will not improve from use of the VACT-CP online intervention. All participants who fail to respond to treatment and request more assistance from research staff, or withdraw prematurely, will be referred for alternative chronic pain therapeutic treatment with the VA..
- 3) Participants in both conditions – intervention and waitlist control- will be regularly monitored for suicide risk throughout the treatment and will receive safety plans as necessary (e.g., VA standard of care for suicide prevention). Thus, all participants will continue to receive the standard of care they would receive were they not enrolled in the study. Assessment of suicide risk will be conducted by a study staff at weeks 3 and 6. Staff will conduct a brief safety assessment and qualitative interview with Veterans assess for potential suicidality, usability issues, and participant health and well-being. During the course of the study, some Veterans may be identified as being at imminent risk for suicide, in which case study staff will follow the suicide risk management plan laid out by the Bedford VA. Given that some study participants may present with numerous vulnerabilities (e.g., history of traumatic brain injury, current or past suicidal ideation or behavior), all study staff members will be trained by Drs. [name] and [name], licensed clinical psychologists, in procedures for conducting risk assessment and crisis

interventions. For participants who in the PI judgment pose a substantial current risk of suicide but do not consent to having a provider contacted, we will breach confidentiality and contact their provider while notifying the participant of this and explaining our rationale (concern for their safety). At the beginning of the study and each subsequent assessment, participants will be told that the information they share is confidential unless the participant appears in jeopardy of harming themselves or someone else. For actively suicidal participants, or other participants who appear at high risk, who are not currently receiving mental health treatment, we will strongly encourage the participant to obtain mental health treatment. In addition, we will make every effort to find treatment for the participant and facilitate their obtaining treatment in a timely way.

